### 11.3.3. Weight

Weight in kilograms (kg) will be measured at every visit except for the telephone visits.

### 11.3.4. Physical Examinations

A complete PE will be conducted at selected study visits (including screening) as shown in the schedule of assessments ([Table 2](#) and [Table 3](#)); at other visits, a symptom-driven PE may be conducted. The complete physical examination will include a general examination of the body, including the abdomen, heart, lungs, lymph nodes, back/neck, neurological system, skin, extremities, head, eyes, nose, and throat.

A symptom-directed physical examination will be conducted throughout the course of the study (except on visits where a complete physical examination will be conducted) following identification of AEs of significant clinical relevance as determined by the investigator.

Clinically significant findings that were present prior to the signing of informed consent must be included in the medical history eCRF. Clinically significant new findings that begin (or pretreatment findings that worsen) after signing the ICF and that meet the definition of adverse events must be recorded on the AE eCRF.

### 11.3.5. Electrocardiogram

TriPLICATE 12-lead ECGs will be performed to evaluate the change from baseline in ECG parameters (heart rate, PR interval, RR interval, QRS duration, QT interval, and QTcF interval). For TDT subjects, ECGs will be obtained at pre-dose and 2 hours ( $\pm 30$  minutes) post-dose at Baseline and at Week 3. For NTDT subjects, ECGs will be obtained at pre-dose and 2 hours ( $\pm 30$  minutes) post-dose at Baseline and at Week 4. At all other timepoints, ECGs will be taken pre-dose.

Interpretation of ECG tracings must be made by a qualified physician and documented on the ECG eCRF(s). The instrument used in the study to assess the ECG should be calibrated per the institution's standard policy.

Clinically significant abnormalities present prior to the subject's signed informed consent should be reported on the medical history eCRF. New or worsened clinically significant findings occurring after informed consent must be recorded on the AE eCRF as described in Section [12.1.2.3](#).

### 11.3.6. Central Laboratory Assessments

Blood and urine samples will be collected for routine clinical safety laboratory assessments according to the schedule of assessments ([Table 2](#) and [Table 3](#)). Clinical safety tests will be assessed to evaluate IMR-687 safety and tolerability.

All abnormal clinical laboratory pages should be initialed and dated by an investigator, along with a comment regarding clinical significance. Each clinically significant laboratory result is to be recorded as medical history at screening and as an AE subsequently. If known, the diagnosis associated with an abnormality in clinical laboratory results considered clinically significant by the investigator should be recorded on the AE eCRF.

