### 11.3.2. Vital Signs

Vital signs include heart rate, respiratory rate, blood pressure, and body temperature. Vital signs should be consistently measured in either the sitting or semi-supine position. Vital signs will be collected at every visit except for the telephone visits. Vital signs will be taken pre-dose and 2 hours ( $\pm 20$  minutes) post-dose on Day 1 and Week 3 for TDT subjects and on Day 1 and Week 4 for NTDT subjects (during PK assessments). At all other timepoints, vital signs can be taken irrespective of taking study drug. Vital signs that are clinically significant and not explained by the underlying disease or concomitant medications should be recorded as AEs in the eCRF.

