## 12. SAFETY MONITORING AND REPORTING

### 12.1.1. Adverse Event and Serious Adverse Event Collection

#### 12.1.1.1. Time Period Adverse Event Collection

All AEs and SAEs, related and unrelated, will be recorded from the signing of informed consent through the end of study safety follow-up visit (Week 40). Events that occur following administration of study drug will be considered TEAEs.

All SAEs will be recorded and reported to the sponsor or sponsor's designee within 24 hours, as indicated in Section 12.1.2.3. The investigator will also submit any updated SAE data to the sponsor within 24 hours of the data being available.

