## 12.1.2.2. Evaluation of Adverse Events/Serious Adverse Events

### 12.1.2.2.1. Assessment of Severity

Adverse event severity (intensity) will be graded using NCI CTCAE, version 5.0 ([Appendix 2](#)). The CTCAE is a descriptive terminology utilized for AE reporting. A grading scale is provided for each AE term.

Grade refers to the severity (intensity) of the AE. The CTCAE provides unique clinical descriptions of severity for each AE based on the following general guideline:

- Grade 1** Mild; asymptomatic or mild symptoms; clinical or diagnostic observations only; intervention not indicated.
- Grade 2** Moderate; minimal, local or noninvasive intervention indicated; limiting age-appropriate instrumental ADL. \*
- Grade 3** Severe or medically significant, but not immediately life-threatening; hospitalization or prolongation of hospitalization indicated; disabling; limiting self-care ADL\*\*.
- Grade 4** Life-threatening consequences: urgent intervention indicated.
- Grade 5** Death related to AE.

ADL = activities of daily living; AE = adverse event; CTCAE = Common Terminology Criteria for Adverse Events

\*Instrumental ADL refer to preparing meals, shopping for groceries or clothes, using the telephone, managing money, etc.

\*\*Self-care ADL refer to bathing, dressing and undressing, feeding self, using the toilet, taking medications, and not bedridden.

Note: The CTCAE terminology provides grading for specific laboratory test abnormalities ([Appendix 2](#)). Grade 4 laboratory abnormalities do not automatically signify life-threatening AEs. Abnormal laboratory test results will be considered AEs only if the investigator, based on his or her medical judgement, deems the abnormality to be clinically significant.

Change in severity of an AE should be documented based on specific guidelines in the eCRF Completion Guidelines.

Severity and seriousness must be differentiated: Severity describes the intensity of an AE, while the term seriousness refers to an AE that has met the criteria for an SAE (defined in Section [12.1.2.1.2](#)).

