10.1.4 Definition of Treatment-Emergence

A treatment-emergent adverse event (TEAE) is defined as an AE that starts after initiation of study drug, or an AE that existed pre-treatment and worsened in severity after initiation of study drug, through 30 days after the last dose of study drug.

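### Protocol 11.3.6 directs AE recording of clinically significant laboratory results after screening even if unchanged, so persistent thalassaemia findings can be counted as TEAEs

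*Protocol*

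**What the plan says.** Four assessment sections of the Protocol each say when a finding becomes an AE.

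- **Laboratory (11.3.6):** "Each clinically significant laboratory result is to be recorded as medical history at screening and as an AE subsequently".
- **Physical examination (11.3.4):** the AE form is for "Clinically significant new findings that begin (or pretreatment findings that worsen) after signing the ICF", provided they meet the AE definition.
- **ECG (11.3.5):** "New or worsened clinically significant findings occurring after informed consent must be recorded on the AE eCRF".
- **Vital signs (11.3.2):** "Vital signs that are clinically significant and not explained by the underlying disease or concomitant medications should be recorded as AEs in the eCRF".

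Protocol 12.1.2.2.1 returns to laboratory abnormalities and says they "will be considered AEs only if the investigator, based on his or her medical judgement, deems the abnormality to be clinically significant".

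Two rules decide whether an AE is treatment-emergent. Protocol 12.1.1.1 says: "Events that occur following administration of study drug will be considered TEAEs". SAP 10.1.4 says: "A treatment-emergent adverse event (TEAE) is defined as an AE that starts after initiation of study drug", and adds a second limb for an AE that was present before treatment and then worsened in severity. SAP 13.6.2.1 and Appendix 3 repeat both limbs.

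**The concern.** The laboratory rule is the only one of the four with no limiting condition beyond clinical significance, and laboratory values are where this disease shows most plainly. NTDT subjects must have Hb of 10.0 g/dL or less at screening. SAP Appendix 4 grades Hb below 10.0 g/dL as Grade 2 anaemia and below 8.0 g/dL as Grade 3. Subjects may also enter with ALT or AST up to 3 x ULN. Raised bilirubin excludes a subject only when direct bilirubin exceeds 3 x ULN and the direct/total ratio exceeds 0.3.

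Incidence and severity of AEs is part of the primary endpoint in both populations. If an unchanged entry abnormality is written up as a new event, the AE tables gain a background unrelated to drug. About 50 sites are planned. A site that follows 11.3.6 literally and a site that carries over the test in 11.3.4 and 11.3.5 would report different rates for identical subjects.

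**Working it through.** The plan states no figure to reproduce, so the check is a comparison of the rules, followed by an illustration of scale.

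**Step 1. Does another section supply the missing condition?**

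| Section | Must be clinically significant? | Further condition |
|---|---|---|
| 11.3.4 Physical examination | Yes | New, or worse than before consent |
| 11.3.5 ECG | Yes | New or worse since consent |
| 11.3.2 Vital signs | Yes | Not explained by the disease or other medication |
| 11.3.6 Laboratory | Yes | None |
| 12.1.2.2.1 Severity (laboratory) | Yes | None |

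No. Section 12.1.2.2.1 repeats the clinical-significance judgement and adds nothing on change from baseline.

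**Step 2. Follow one unchanged value through the rules.** Take an NTDT subject whose Hb stays at 7.8 g/dL (an illustrative value, Grade 3 in Appendix 4) and whose investigator calls it clinically significant.

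1. *Screening:* it goes to medical history. No AE record is created.
2. *Day 1, before dosing:* haematology is drawn again, and read literally 11.3.6 now makes it an AE. If its onset is recorded as before the first dose, it is not a TEAE unless it worsens. If it is dated Day 1 with no onset time, SAP Appendix 3 makes it a TEAE.
3. *Week 1 onward:* if it is entered with the visit date as onset, it meets the first limb of SAP 10.1.4 and is a TEAE. If it is entered with its true, earlier onset, it is pre-treatment and unchanged, so it is not.
4. *Status undeterminable:* SAP 13.6.2.1 defaults to treatment-emergent.

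The worsening limb needs a pre-treatment AE to compare with. The screening finding was sent to medical history, and neither SAP 13.6.2.1 nor Appendix 3 checks against that form. Protocol 12.1.1.1 has no worsening limb at all.

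**Step 3. Opportunities.** The schedules give 11 haematology/chemistry draws after Day 1 in NTDT (Weeks 1, 4, 8, 12, 16, 20, 24, 28, 32, 36, 40) and 9 in TDT (Weeks 1, 3, 6, 12, 18, 24, 30, 36, 40). SAP 13.6.2.1 counts a subject once per SOC or PT. One such entry is therefore enough to count the subject, and repeat entries at later draws add nothing to incidence.

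**Step 4. Scale, by assumption only.** Let s be the share of subjects with an unchanged finding that ends up as a TEAE, and p the true any-TEAE rate. If the two are independent and s is equal across arms, the observed rate is 1 - (1 - p)(1 - s), and a risk difference is multiplied by (1 - s). For an assumed p of 50% on drug and 30% on placebo:

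| s (assumed) | Drug | Placebo | Difference |
|---|---|---|---|
| 0 | 50% | 30% | 20 points |
| 0.3 | 1 - 0.5 x 0.7 = 65% | 1 - 0.7 x 0.7 = 51% | 14 points |
| 0.8 | 1 - 0.5 x 0.2 = 90% | 1 - 0.7 x 0.2 = 86% | 4 points |

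Neither s nor p is in the documents. The table shows the direction of the effect and how it depends on s; it is not an estimate.

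**The case against.** A reader might infer from 11.3.6 that unchanged thalassaemia findings automatically become TEAEs in every arm. The documents do not support that. Two things must happen first. The investigator must judge the value clinically significant, and may well not do so for a low Hb in a subject enrolled because of it. The event must also be given a post-dose, untimed Day 1 or undeterminable onset. An AE dated before dosing that does not worsen is not a TEAE under the SAP, and the Day 1 pre-dose draw gives sites a natural point at which to date it correctly. Protocol 11.1.2 also asks for baseline severity of concurrent signs and symptoms to be documented. All of this stands, and it is why s can be 0.

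The consequences are also limited:

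- Safety analysis is descriptive, so no test loses power.
- An unchanged disease finding fits the unlikely/not related category of Protocol 12.1.2.2.2, so the treatment-related TEAE and treatment-related Grade 3+ tables should largely escape.
- The SAP separately reports clinically significant worsening in CTCAE laboratory grade, shifts from baseline to maximum grade, and change from baseline. All three compare with the subject's own baseline.

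The eCRF Completion Guidelines, which Protocol 12.1.2.2.1 cites for changes in AE severity, are not among the documents and may already cover persistent findings.

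What survives is that the rule as written omits a condition its neighbours carry. The SAP filter works only when onset is dated before dosing, and its defaults for unknown onset run toward treatment-emergent.

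**Conclusion.** The point holds in a limited form. Read literally, 11.3.6 directs AE recording of unchanged clinically significant laboratory results, and nothing else in the Protocol restores the new-or-worsened condition. Such an entry can reach the TEAE tables, depending on clinical judgement and onset dating. The rows exposed are any TEAE, Grade 3 or higher TEAEs, and the anaemia and bilirubin terms.

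The size is unknown. It starts at 0% of subjects, and the documents fix no upper value. The shrinkage from 20 points to 14 or 4 should not be read as a finding, because it rests wholly on assumed s and p, on independence, and on equal inflation across arms. Equal inflation is a reasonable expectation under blinding but is not guaranteed. The more certain cost is inconsistency: sites have grounds in the Protocol's own text for recording the same finding differently. The change is worth making because AE incidence is a primary measure and the repair is small.

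**What to change.** Make three linked changes.

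1. **Reword 11.3.6.** Clinically significant results present before the first dose are medical history, or a pre-treatment AE if they arise after consent. After the first dose, only results that are new or worsened from baseline are recorded as AEs. This follows the principle in 11.3.4 and 11.3.5, but those sections count from consent, so the new text should name baseline explicitly.
2. **State how onset is dated.** A persistent finding carries its original onset date, not the date of the visit at which it was next seen. Without this, the SAP's worsening limb cannot work.
3. **Align the TEAE sentence in 12.1.1.1 with SAP 10.1.4,** including the worsening limb.

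The cost is a short protocol amendment and a matching change to the eCRF guideline. No new data are collected. The study is already under way, so an amendment needs the ethics and regulatory approvals in Protocol 15.1.1 before sites apply it. Laboratory AEs already recorded under the present text should be reviewed for onset date by staff blinded to treatment.

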#### 11.3.6.1. Hematology

Hematology assessments will be performed through a central laboratory and will include the following: RBC count (mean corpuscular volume [MCV], mean corpuscular Hb, and mean corpuscular Hb concentration), hematocrit (Hct), Hb, platelets, WBC count (with differential: basophils, eosinophils, neutrophils, monocytes, and lymphocytes), erythrocyte count, reticulocyte count, and reticulocyte percentage. Some of these assessments are also considered PD endpoints (refer to [Section 11.2](#)).

#### 11.3.6.2. Coagulation

Coagulation assessments will include PT, aPTT, and INR. Some of these assessments are also considered PD endpoints (refer to [Section 11.2](#)).

#### 11.3.6.3. Serum Chemistry

Serum chemistries will be performed through a central laboratory and will include but not be limited to the following: ALT, albumin, alkaline phosphatase (ALP), AST, bicarbonate, blood urea nitrogen (BUN), chloride, calcium, creatinine, glucose, LDH, sodium, potassium, magnesium, phosphate, bilirubin (total, direct, and indirect), creatine kinase, total protein, glomerular filtration rate (GFR), and gamma-glutamyl transferase. FSH is added for post-menopausal women at screening. Some of these assessments are also considered PD endpoints (refer to [Section 11.2](#)).

#### 11.3.6.4. Urinalysis

Urine will be assessed for appearance, color, pH, specific gravity, ketone, protein, glucose, bilirubin, and urobilinogen, including occult blood and microscopic examination of sediment (only if occult blood is detected).

#### 11.3.6.5. Pregnancy Test

Serum pregnancy tests will be performed during screening via a central laboratory for all female subjects of childbearing potential who are not post-menopausal or surgically sterile. All subsequent pregnancy tests will be urine pregnancy tests performed locally (with test kits provided by the central laboratory). If a urine pregnancy test is positive, the result must be confirmed with a serum pregnancy test.

### **11.3.7. Adverse Event Collection**

Details of AE data collection are described in Section [12](#). Adverse events will be collected at every visit.

### **11.3.8. Concomitant Medications**

Concomitant medications will be recorded at every visit in the medical record and on the appropriate eCRF. Any additions, discontinuations, or changes of these medications will be documented.

## **11.4. Pharmacokinetic Assessments**

### **11.4.1. Plasma Pharmacokinetics**

Serial blood samples will be collected at the timepoints indicated in the schedule of assessments ([Table 2](#) and [Table 3](#)) for determination of IMR-687 concentration (including metabolites). At Baseline (all subjects) and Week 3 (TDT subjects) or Week 4 (NTDT subjects), serial blood samples will be drawn pre-dose (within 30 minutes) and at 15 minutes ( $\pm 5$  minutes), 30 minutes ( $\pm 5$  minutes), and 3 hours ( $\pm 20$  minutes) after administration of study drug. A trough blood sample will be drawn pre-dose at Week 1, Week 24, and Week 36. The date/time of the previous dose will be recorded.

Refer to the laboratory manual for details on the collection, handling, and processing of blood samples.

## 12. SAFETY MONITORING AND REPORTING

### 12.1.1. Adverse Event and Serious Adverse Event Collection

#### 12.1.1.1. Time Period Adverse Event Collection

All AEs and SAEs, related and unrelated, will be recorded from the signing of informed consent through the end of study safety follow-up visit (Week 40). Events that occur following administration of study drug will be considered TEAEs.

All SAEs will be recorded and reported to the sponsor or sponsor's designee within 24 hours, as indicated in Section 12.1.2.3. The investigator will also submit any updated SAE data to the sponsor within 24 hours of the data being available.

#### 12.1.1.2. Follow-up

After the initial AE/SAE report, the investigator is required to proactively follow each subject at subsequent visits and phone contacts. All SAEs will be followed until resolution, stabilization, the event is otherwise explained, or the subject is lost to follow-up.

### 12.1.2. Adverse Event Recording and Reporting

#### 12.1.2.1. Definitions

##### 12.1.2.1.1. Definition of an Adverse Event

An AE is defined as any untoward medical occurrence in a clinical study subject administered a pharmaceutical product and which does not necessarily have to have a causal relationship with this treatment. An AE can therefore be any unfavorable or unintended sign (for example, an abnormal laboratory finding), symptom, or disease temporally associated with the use of a medicinal (investigational) product, whether or not considered related to the medicinal (investigational) product.

Examples of AEs include but are not limited to:

- Abnormal test findings
- Clinically significant symptoms and signs
- Changes in physical examination findings
- Hypersensitivity
- Drug abuse
- Drug dependency

Additionally, they may include the signs or symptoms resulting from:

- Drug overdose
- Drug withdrawal
- Drug misuse

- Drug interactions
- Extravasation
- Exposure during pregnancy
- Exposure via breastfeeding
- Medication error

#### **12.1.2.1.2. Definition of a Serious Adverse Events**

An SAE is any AE that results in one or more of the following outcomes:

- **Death**
- **Requires or prolongs hospitalization** (In general, hospitalization signifies that the subject has been detained, usually involving at least an overnight stay, at the hospital or emergency ward for observation and/or treatment that would not have been appropriate in the physician's office or outpatient setting. Complications that occur during hospitalization are AEs. If a complication prolongs hospitalization or fulfills any other serious criteria, the event is serious. When in doubt as to whether "hospitalization" occurred or was necessary, the AE should be considered serious.)
- **Is life-threatening** (In general, an AE is considered to be life-threatening if the subject is at immediate risk of death. It does not include an AE that, had it occurred in a more severe form, might have caused death.)
- **Persistent or significant disability/incapacity** (In general, this means a substantial disruption of a person's ability to conduct normal life functions. This definition is not intended to include experiences of relatively minor medical significance such as uncomplicated headache, nausea, vomiting, diarrhea, influenza, or accidental trauma [e.g., sprained ankle] that may interfere with or prevent everyday life functions, but do not constitute a substantial disruption.)
- **Congenital anomaly or birth defect** (that occurs in the offspring of a subject exposed to the investigational product)
- **Other medically important event** (In general, this means an AE that based upon appropriate medical judgment is considered to jeopardize the subject's safety and may require medical or surgical intervention to prevent one of the outcomes listed above.)

Reporting requirements for SAEs are described in Section [12.1.2.3](#).

#### **12.1.2.1.3. Definition of a Suspected Unexpected Serious Adverse Reaction**

A suspected unexpected serious adverse reaction (SUSAR) is an SAE that, in the opinion of the investigator, is believed with reasonable probability (i.e., suspected) to be due to the investigational product, but the nature or severity of which is not consistent with the reference safety information (i.e., is unexpected).

Reporting requirements for SUSARs are described in Section [12.1.2.4](#).

## 12.1.2.2. Evaluation of Adverse Events/Serious Adverse Events

### 12.1.2.2.1. Assessment of Severity

Adverse event severity (intensity) will be graded using NCI CTCAE, version 5.0 ([Appendix 2](#)). The CTCAE is a descriptive terminology utilized for AE reporting. A grading scale is provided for each AE term.

Grade refers to the severity (intensity) of the AE. The CTCAE provides unique clinical descriptions of severity for each AE based on the following general guideline:

- Grade 1** Mild; asymptomatic or mild symptoms; clinical or diagnostic observations only; intervention not indicated.
- Grade 2** Moderate; minimal, local or noninvasive intervention indicated; limiting age-appropriate instrumental ADL. \*
- Grade 3** Severe or medically significant, but not immediately life-threatening; hospitalization or prolongation of hospitalization indicated; disabling; limiting self-care ADL\*\*.
- Grade 4** Life-threatening consequences: urgent intervention indicated.
- Grade 5** Death related to AE.

ADL = activities of daily living; AE = adverse event; CTCAE = Common Terminology Criteria for Adverse Events

\*Instrumental ADL refer to preparing meals, shopping for groceries or clothes, using the telephone, managing money, etc.

\*\*Self-care ADL refer to bathing, dressing and undressing, feeding self, using the toilet, taking medications, and not bedridden.

Note: The CTCAE terminology provides grading for specific laboratory test abnormalities ([Appendix 2](#)). Grade 4 laboratory abnormalities do not automatically signify life-threatening AEs. Abnormal laboratory test results will be considered AEs only if the investigator, based on his or her medical judgement, deems the abnormality to be clinically significant.

Change in severity of an AE should be documented based on specific guidelines in the eCRF Completion Guidelines.

Severity and seriousness must be differentiated: Severity describes the intensity of an AE, while the term seriousness refers to an AE that has met the criteria for an SAE (defined in Section [12.1.2.1.2](#)).

